25.7.4 Method of Detecting AEs and SAEs

- Care should be taken not to introduce bias when detecting AE and/or SAE

- Patient reported outcomes/clinical outcome assessment surveys will be the method for detecting and reporting of adverse events

25.7.5 Recording and Follow-up of AEs and SAEs

- When an AE/SAE occurs, it is the responsibility of the Investigator to review all documentation (e.g., hospital progress notes, laboratory, and diagnostics reports) related to the event. The Investigator will then record all relevant AE/SAE information. It is required for the Investigator to send photocopies or digital files of the participant's medical records to Sponsor in addition to completion of the required AE/SAE form. There may be instances when medical records for certain cases are requested by pharmacovigilance staff. In this case, all participant identifiers, with the exception of the participant number, will be redacted on the copies of the medical records before submission.
- The investigator will attempt to establish a diagnosis of the event based on signs, symptoms, and/or other clinical information. Whenever possible, the diagnosis (not the individual signs/symptoms) will be documented as the AE/SAE.
- After the initial AE/SAE report, the Investigator is required to proactively follow each participant at subsequent visits/contacts. All SAEs and non-serious AEs of special interest will be followed until the event is resolved, stabilized, otherwise explained, or the participant is lost to follow-up. Further information on follow-up procedures is given in this document.
- The Investigator is obligated to perform or arrange for the conduct of supplemental measurements and/or evaluations as medically indicated or as requested by pharmacovigilance to elucidate the nature and/or causality of the AE or SAE as fully as possible. This may include additional laboratory tests or investigations, histopathological examinations, or consultation with other health care professionals. If a participant dies during participation in the study or during a recognized follow-up period, the Investigator will provide sponsor with a copy of any post-mortem findings including histopathology. New or updated information will be recorded in the participant's medical record and submitted as supplemental information to the original report. The Investigator will submit any updated SAE data to the sponsor or designee within 24 hours of receipt of the information.

25.7.6 Assessment of Event Intensity

The Investigator will make an assessment of intensity for each AE and SAE reported during the study and assign it to 1 of the following categories:

- Mild: An event that is easily tolerated by the participant, causing minimal discomfort and not interfering with everyday activities.
- Moderate: An event that causes sufficient discomfort and interferes with normal everyday activities.
- Severe: An event that prevents normal everyday activities. An AE that is assessed as severe should not be confused with an SAE. Severe is a category utilized for rating the intensity of an event; and both AE and SAE can be assessed as severe.

An event is defined as ‘serious’ when it meets at least 1 of the predefined outcomes as described in the definition of an SAE, NOT when it is rated as severe.

25.7.7 Assessment of Causality

The Investigator is obligated to assess the relationship between study intervention and each occurrence of each AE/SAE.

- A "reasonable possibility" of a relationship conveys that there are facts, evidence, and/or arguments to suggest a causal relationship, rather than a relationship cannot be ruled out.
- The Investigator will use clinical judgment to determine the relationship.
- Alternative causes, such as underlying disease(s), concomitant therapy, and other risk factors, as well as the temporal relationship of the event to study intervention administration will be considered and investigated.
- The Investigator will also consult the Product Information (Package Insert), for marketed products, in his/her assessment.
- For each AE/SAE, the Investigator **must** document in the participant’s medical record that he/she has reviewed the AE/SAE and has provided an assessment of causality.
- There may be situations in which an SAE has occurred and the Investigator has minimal information to include in the initial report to sponsor. However, **it is very important that the Investigator always make an assessment of causality for every event before the initial transmission of the SAE data to Sponsor.**
- The Investigator may change his/her opinion of causality in light of follow-up information and send an SAE follow-up report with the updated causality assessment.
- The causality assessment is one of the criteria used when determining regulatory reporting requirements.

25.8 Recording and Reporting Adverse Events

- For the purpose of processing and reporting adverse events, the study period is defined as that time period from signature of the informed consent form through the last visit of the study. AEs may be reported by the study participant (or, when appropriate, by a caregiver, surrogate, or the participant's legally authorized representative), the PI or the Study Coordinator.
- Reporting of non-serious adverse events will be limited to **ONLY** the following:
 - Any event reported by the patient on his/her follow-up survey in the first 24 hours post-administration of AZD7442
 - Any event reported by the patient on his/her follow-up survey that includes an unplanned telehealth visit, unscheduled physician office visit, ER/Urgent Care Visit
 - Any positive SARS-CoV-2 test by RT-PCR reported to the study site
 - Any symptoms of SARS-CoV-2 reported by the patient on any follow-up survey
 - If the Investigator considers that there was a causal relationship between treatment with AZD7442 or protocol design/procedures and a patient's underlying disease progression, then this must be reported as an AE or SAE.
- All AEs will be collected from baseline AZD7442 administration through day 360 post-baseline. SAEs will be collected from dose administration through the day 360 follow-up visit at the time points specified in the Schedule of Activities. However, any SAEs assessed as related to study participation (e.g., study intervention, protocol-mandated procedure, invasive tests or change in existing therapy) will be recorded from the time participant consents to participate in the study.
- Medical occurrences that begin before the start of study intervention but after obtaining Informed Consent will be recorded as Medical History/Current Medical Conditions not as AEs.
- All SAEs will be recorded and reported to the Sponsor or designee immediately and under no circumstance should this exceed 24 hours. The Investigator will submit any updated SAE data to the Sponsor or designee within 24 hours of it being available.
- Investigators are not obligated to actively seek information on AEs or SAEs after the conclusion of study participation. However, if the investigator learns of any SAE, including a death, at any time after a participant has been discharged from the study, and he/she

considers the event to be reasonably related to the study intervention or study participation, the Investigator must promptly notify the sponsor or designee.

- The primary mechanism for reporting SAEs will be the digital SAE Report Form. The site will use the digital SAE data collection tool to report the event within 24 hours. Details to be provided in the Study Specific SAE Reporting Guidelines. The Investigator must show evidence of review and verification of the relationship of each SAE to IP/study participation (causality) within 24 hours of SAE identification. If a site receives a report of a new SAE from a study participant or receives updated data on a previously reported SAE, then the site can report this information on the digital SAE form or to the Sponsor by telephone or e-mail. Contacts for SAE reporting will be included in the Study Specific SAE Reporting Guidelines.
- All SAEs reported to the Sponsor (MediMergent) will simultaneously or not later than 24 hours following receipt by the Sponsor, be reported by the Sponsor to AstraZeneca.

25.9 Expedited Reporting

- Sponsor will promptly evaluate all serious adverse events and non-serious adverse events to identify and expeditiously communicate new safety findings to Investigators, IRBs, ECs, and health authorities based on applicable requirements as per the Safety Reporting Plan.
- To determine reporting requirements for single adverse event cases, Sponsor's Medical Monitor will assess the expectedness of these events using the AZD7442 Investigator Brochure and FDA approved prescribing information.
- All Sudden Unexpected Serious Adverse Events (SUSARs) will be submitted by MediMergent to the FDA. MediMergent will simultaneously send a copy of the initial SUSAR report and all follow-up reports to AstraZeneca.
- Where expedited reporting is described, the sponsor will submit SUSARs to FDA within FDA required timelines for IND reports.

25.10 Study Medication

- All adverse events that occur during the defined study period must be recorded in the patients' medical record regardless of the severity of the event or judged relationship to study medication. All reported or observed signs and symptoms will be recorded individually, except when considered manifestations of a medical condition or disease state.
- A precise diagnosis will be recorded whenever possible. When such a diagnosis is made, all related signs, symptoms, and any test findings will be recorded collectively as a single

diagnosis. The onset and end dates, duration (in case of adverse event duration less than 24 hours), action taken regarding study drug, treatment administered, and outcome for each adverse event should be recorded in the patients' medical record.

25.11 Severity of an Adverse Event

- Standard toxicity grading according to the DAIDS Table for Grading the Severity of Adult and Pediatric Adverse Events, version 2.1 (July 2017) will be used to grade all AEs.
- The severity of each adverse event must be recorded as 1 of the choices on the following scale:
 - Mild: An event that is easily tolerated by the participant, causing minimal discomfort and not interfering with everyday activities.
 - Moderate: An event that causes sufficient discomfort and interferes with normal everyday activities.
 - Severe: An event that prevents normal everyday activities. An AE that is assessed as severe should not be confused with an SAE. Severe is a category utilized for rating the intensity of an event; and both AE and SAE can be assessed as severe.

25.12 Relationship of an Adverse Event to AZD7442

The relationship of an adverse event to AZD7442 is characterized as follows:

Definition of Adverse Event Relationship to AZD7442

Term	Definition	Clarification
No reasonable possibility (not related)	This category applies to those adverse events which, after careful consideration, are clearly due to extraneous causes (disease, environment, etc.) or to those adverse events, which, after careful medical consideration at the time they are evaluated, are judged to be unrelated to AZD7442.	The relationship of an adverse event to AZD7442 may be considered to have no reasonable possibility if it is clearly due to extraneous cause(s) such as: 
 • it does not follow a reasonable temporal sequence from the administration of AZD7442. • it could readily have been produced by the patient’s clinical state, environmental or toxic factors, or other modes of therapy administered to the patient.
Reasonable possibility (related)	This category applies to those adverse events for which there is evidence to suggest a causal relationship between the drug and the adverse even after careful medical consideration at the time they are evaluated, a connection with AZD7442 administration was felt with a high degree of certainty to be related to AZD7442.	The relationship of an adverse event to AZD7442 may be considered reasonable possibility related if: 
 • it follows a reasonable temporal sequence from administration of AZD7442 and/or • conveys in general that there are facts (evidence) or arguments to suggest a causal relationship.

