18.5 Hospitalization and Deaths

For purposes of this study, all hospitalizations and/or deaths will be considered a SAE. Hospitalization for a pre-existing condition that has not worsened (i.e., change a pacemaker battery) or for elective surgery will NOT be considered a SAE unless the hospitalization is prolonged by related SARS-CoV-2 therapy complications. These events will be collected and reported as SAEs only if the event is more severe than expected for the participant's current clinical status and medical history or if the Investigator feels that it is related to study drug. These will be collected and reported as SAEs as delineated below. Since it will not be possible to delineate in a single participant whether the hospitalization is directly related to SARS-CoV-2 infection complications, their underlying cancer, treatment for this cancer or could be related to AZD7442 causing more severe disease due to ADE, all hospitalizations for management of acute illness, regardless of cause, will be sent for evaluation to the Clinical Events Committee (CEC). See Section 20.1.

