25.13.3 Expectedness

- A SAE that is not included in the Adverse Reaction section of the relevant reference safety information by its specificity, severity, outcome, or frequency is considered an unexpected adverse event.

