25.14 Disease-Related Events and/or Disease-Related Outcomes Not Qualifying as AEs or SAEs

Adverse events related to signs, symptoms or positive RT-PCR testing for SARS-CoV-2 infection, and/or resulting in hospitalization should be reported as an AE or SAE. If the Investigator considers that there was a causal relationship between treatment with AZD7442 or protocol design/procedures and a patient's underlying disease progression, then this must be reported as an AE or SAE.

For example, the following constitute events meeting the AE definition and that should be considered as expected progression, signs, or symptoms of COVID-19:

- hypoxemia requiring supplemental oxygen
- hypoxemia requiring non-invasive ventilation or high flow oxygen devices
- respiratory failure requiring invasive mechanical ventilation or extracorporeal membrane oxygenation (ECMO)

NOTE: If either of the following conditions apply, then the event must be recorded and reported as an AE or SAE (instead of a disease-related event):

- The event is, in the Investigator's opinion, of greater intensity, frequency, or duration than expected for the natural history of the disease, or
- The Investigator considers that there is a reasonable possibility that the event was related to treatment with study treatment(s).

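### Protocol 25.12 defines a related adverse event with a near-certainty phrase that contradicts 25.7.7, the clarification in its own table row, and the category's own label

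*Protocol*

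**What the plan says.** The protocol describes the causality threshold in several places.

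- **25.12, Definition column, related row.** It opens with a low bar, "evidence to suggest a causal relationship between the drug and the adverse even after careful medical consideration", and runs straight on, with no joining word, to a high one: "a connection with AZD7442 administration was felt with a high degree of certainty to be related to AZD7442".
- **25.12, Clarification column, same row.** An event may be considered related if "it follows a reasonable temporal sequence from administration of AZD7442 and/or" there are facts or arguments pointing to causality.
- **25.12, not-related row.** Among the examples of a clearly extraneous cause is an event readily explained by the patient's clinical state, "environmental or toxic factors, or other modes of therapy administered to the patient".
- **25.7.7.** A reasonable possibility "conveys that there are facts, evidence, and/or arguments to suggest a causal relationship, rather than a relationship cannot be ruled out". The investigator decides by clinical judgment, and the result is one of the criteria for regulatory reporting.
- **18.5, repeated in nearly the same words in 25.3.** "Since it will not be possible to delineate in a single participant whether the hospitalization is directly related to SARS-CoV-2 infection complications", the cancer, its treatment, or AZD7442 acting through ADE, every hospitalization for acute illness goes to the Clinical Events Committee (CEC).
- **25.14.** The heading concerns events that do not qualify as AEs or SAEs. The first sentence says that SARS-CoV-2 signs, symptoms, positive RT-PCR tests and hospitalizations should be reported as AEs or SAEs. Oxygen requirement, ventilation and ECMO are then said both to meet the AE definition and that they "should be considered as expected progression, signs, or symptoms of COVID-19". A NOTE has an event reported as an AE or SAE, rather than as a disease-related event, if it is worse than the natural history or there is a reasonable possibility that it is related to treatment.

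**The concern.** The scale has only two levels, so the wording of the boundary decides every event of intermediate likelihood. A bar near certainty and a bar of suggestive evidence place those events on opposite sides. The table gives both bars in one row.

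Two things depend on the code. It contributes to deciding which serious events are expedited as SUSARs (25.7.7, 25.9). It is also the natural source for the secondary endpoint in 14.1 that compares AZD7442-related side effects between solid tumor and hematologic malignancy patients.

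Every patient receives active drug (5.1). No concurrent control arm can show an excess of events if individual attribution is miscoded. With up to 75 locations (6.1), a threshold that depends on which sentence a site follows adds avoidable variation, and the certainty phrase pulls in one direction.

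**Working it through.** No arithmetic applies, because the point depends on no rate, error level or sample size. The check is a comparison of the texts.

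1. **Definition against label.** The category is called a reasonable possibility. A connection held with near certainty is a much stronger state of belief, so the definition does not fit its name.

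2. **Definition against 25.7.7.** Section 25.7.7 explains the same term and asks for supporting facts, evidence or arguments. It requires no certainty. An event with suggestive but inconclusive evidence is related under 25.7.7 and is not related if the certainty phrase is applied.

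3. **Definition against the adjacent clarification.** The joining words are and/or, so plausible timing alone is enough on a literal reading. That is looser than 25.7.7, while the certainty phrase is stricter. The row therefore departs from 25.7.7 in both directions.

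4. **Overlap with the not-related row.** Many events in treated cancer patients have a ready explanation in the disease or its therapy and also follow dosing in plausible sequence. Such an event can match the examples in both rows, and the table does not say which prevails.

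5. **ADE hospitalizations.** Section 18.5 says the candidate causes cannot be separated in one participant. A site that demanded near certainty could hardly reach it for such an event and would tend towards not related. Referral to the CEC does not clearly close the gap. Its remit in 20.1 and 25.22 covers relatedness to SARS-CoV-2, clinical events and severity, and relatedness to AZD7442 is not mentioned.

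6. **25.14 against itself and 25.7.2.** Section 25.7.2 makes COVID-19 symptoms and a positive PCR test AEs without condition, and the first sentence of 25.14 agrees. The heading and the NOTE suggest that some of these events are reported as AEs or SAEs only on further conditions. One of those conditions is the term that 25.12 defines inconsistently.

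7. **What is unaffected.** All SAEs go to the sponsor regardless of judged relationship (25.13.6), and the sponsor evaluates serious and non-serious events for new findings (25.9). The exposure is limited to the causality code and what is derived from it.

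**The case against.** The strongest reply is that the related definition is a garbled sentence, not a strict rule. It begins with the low bar and has lost at least a letter. The parallel not-related definition joins its two limbs with the word or. If an or was dropped here too, near certainty is one route to the related code and not a condition for it. This is plausible. It shows that the text does not make certainty a necessary condition. It does not remove the contradiction, because a site has to read the table as printed.

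A reader might infer more than the documents support:

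- **That an ADE hospitalization can never be coded related.** Section 18.5 explains why cases go to the CEC and does not address the causality code. The clarification column, 25.7.7 and 25.14 each allow the related code without certainty.
- **That events of middling likelihood default to not related.** The ready-alternative example is governed by wording about clearly extraneous causes and by a permissive may. The protocol states no default.
- **That the ADE signal drops out of expedited reporting.** Serious events still reach the sponsor whatever their code, and causality is only one reporting criterion. The Data Monitoring Committee also reviews adverse events at the interim analysis, with attention to RT-PCR positives (21.1).
- **That 25.14 overrides regulatory expectedness.** Its phrase describes the course of the disease. Regulatory expectedness is set in 25.9 and in 25.13.3, which starts from "A SAE that is not included in the Adverse Reaction section of the relevant reference safety information". These are two different uses of the word expected.

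Two further replies stand in part. Section 14.1 does not say that the side-effect endpoint is derived from the 25.12 code, so that link is an inference, though a natural one. And 25.7.7 itself excludes relationships that merely cannot be ruled out, so adopting it would not automatically make an inseparable ADE hospitalization related.

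**Conclusion.** The point holds as a contradiction in the rule that investigators use to code causality. The 25.12 definition does not fit 25.7.7, the clarification beside it, or its own label. The consequence is coding that can differ between sites, with a tendency to under-attribution wherever the certainty phrase is followed. Possible ADE hospitalizations are the most exposed.

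The size cannot be quantified. The documents do not say how many sites would follow which wording, or how many suspected reactions are of intermediate likelihood. Any percentage would only return what had been assumed.

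The conclusion rests on two assumptions: that some sites would apply the certainty phrase as written, and, for the endpoint, that related side effects are taken from this code. The unclear status of COVID-19 events in 25.14 is a smaller, connected fault. This should be corrected, because the wording is wrong as it stands and bears on safety reporting.

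**What to change.** 1. In 25.12, delete the certainty phrase and use the 25.7.7 definition of a reasonable possibility in both columns of the related row.
2. In the not-related row, state that a merely possible alternative cause does not by itself make an event not related.
3. In 25.14, reconcile the heading and the NOTE with the first sentence and with 25.7.2, so that RT-PCR-positive COVID-19 events are unambiguously reported as AEs or SAEs.

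The cost is a wording amendment to one table and one section, brief retraining of sites, and possibly more events coded related, with some additional reports for the sponsor to assess.
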